10.1.4 Pregnancy reporting

Pregnancies

To ensure subject safety, each pregnancy occurring after signing the informed consent must be reported to Novartis within 24 hours of learning of its occurrence. The pregnancy should be followed up to determine outcome, including spontaneous or voluntary termination, details of the birth, and the presence or absence of any birth defects, congenital abnormalities, or maternal and/or newborn complications.

Pregnancy should be recorded and reported by the investigator to the Novartis Chief Medical Office and Patient Safety (CMO&PS). Pregnancy follow-up should be recorded on the same form and should include an assessment of the possible relationship to the study treatment. Any SAE experienced during pregnancy must be reported. Information will be collected at three time points after the estimated date of delivery and for a period of 12 months.

Follow up of the pregnancy (female participant) should be according to the following schedule:

Tracking of pregnancy cases occurs until after Expected Delivery Date (EDD) for all prospective pregnancy cases received from clinical studies (including pregnancies where the participant was exposed to placebo and pregnancies due to the conduct of the study).

- EDD + 1 month (mandatory for all cases). Requesting the pregnancy outcome and other clinically relevant pregnancy data or changes in data.
- EDD + 2 month (mandatory if no answer is obtained after request at EDD+1 month). A reminder letter for the outcome.
- The follow-up at EDD + 3 months is mandatory for all cases of live birth. Information on the status of the baby 3 months after delivery and information on any development issue or abnormality that would not be seen at birth must be collected.
- The follow up at EDD + 12 months is mandatory for all cases of live birth. Information on the status of the baby 12 months after delivery and information on any development issue or abnormality that would not be seen at birth must be collected. If the pregnancy case is lost to follow-up (e.g., no response after 3 attempts) this information must be transferred to the Safety Desk of the Country participant Safety.

10.1.5 Reporting of study treatment errors including misuse/abuse

Medication errors are unintentional errors in the prescribing, dispensing, administration or monitoring of a medicine while under the control of a healthcare professional, participant or consumer (EMA definition).

Misuse refers to situations where the medicinal product is intentionally and inappropriately used not in accordance with the protocol.

Abuse corresponds to the persistent or sporadic, intentional excessive use of a medicinal product, which is accompanied by harmful physical or psychological effects.

Study treatment errors and uses outside of what is foreseen in the protocol will be recorded on the appropriate CRF irrespective of whether or not associated with an AE/SAE and reported to Safety only if associated with an SAE. Misuse or abuse will be collected and reported in the safety database irrespective of it being associated with an AE/SAE within 24 hours of Investigator's awareness.

| misuse/abuse | | | |
|-------------------------------------|------------------------------------|-------------------------------|---|
| Treatment error type | Document in Dosing CRF (Yes/No) | Document in AE eCRF | Complete SAE form |
| Unintentional study treatment error | Yes | Only if associated with an AE | Only if associated with an SAE |
| Misuse/Abuse | Yes | Yes | Yes, even if not associated with a SAE |

Confidential

Cuidenes for conturing the study treatment errors including Table 10 1

For more information on AE and SAE definition and reporting requirements, please see the respective sections.

10.2 Additional Safety Monitoring

10.2.1 Liver safety monitoring

To ensure participant safety and enhance reliability in determining the hepatotoxic potential of an investigational drug, a standardized process for identification, monitoring and evaluation of liver events has to be followed

The following two categories of abnormalities / AEs have to be considered during the course of the study (irrespective of whether classified/reported as AE/SAE):

- Liver laboratory triggers, which will require repeated assessments of the abnormal laboratory parameter
- Liver events, which will require close observation, follow-up monitoring and completion of the standard base liver CRF pages

Please refer to Section 16.2 for complete definitions of liver laboratory triggers and liver events.

Once a participant is exposed to study treatment, every liver event defined in Section 16.2 should be followed up by the investigator or designated personnel at the trial site, as summarized below. Additional details on actions required in case of liver events are outlined in Section 16.2. Repeat liver chemistry tests (i.e. ALT, AST, total bilirubin (TBL), prothrombin time(PT)/international Normalized Ratio (INR), ALP and GGT) to confirm elevation.

- These liver chemistry repeats will be performed using the central laboratory. If results will • not be available from the central laboratory, then the repeats can also be performed at a local laboratory to monitor the safety of the participant. If a liver event is subsequently reported, any local liver chemistry tests previously conducted that are associated with this event should have results recorded on the appropriate CRF.
- If the initial elevation is confirmed, close observation of the participant will be initiated, • including consideration of treatment interruption if deemed appropriate.
- Discontinuation of the investigational drug (refer to the Discontinuation of study treatment ٠ section), if appropriate
- Hospitalization of the participant if appropriate •
- Causality assessment of the liver event •
- Thorough follow-up of the liver event should include •

• These investigations can include based on investigator's discretion: serology tests, imaging and pathology assessments, hepatologist's consultancy; obtaining more detailed history of symptoms and prior or concurrent diseases, history of concomitant drug use, exclusion of underlying liver disease

All follow-up information and procedures performed must be recorded as appropriate in the eCRF.

10.2.2 Renal safety monitoring

There has been no safety signal for nephrotoxicity with secukinumab to participants and healthy participants exposed, and from a mechanism of action standpoint there is no known effect of blocking IL-17A on the kidney. All participants with laboratory tests containing clinically significant abnormal values (see Section 16.1) are to be followed until the values return to normal ranges or until a valid reason, other than treatment related AE, is defined. Standard renal function tests (blood urea nitrogen, serum creatinine) will be obtained at regular intervals, but special measures for renal safety monitoring are not planned.

11 Data Collection and Database management

11.1 Data collection

Designated investigator staff will enter the data required by the protocol into the eCRF. The eCRFs have been built using fully validated secure web enabled software that conforms to 21 CFR (Code of Federal Regulation) Part 11 requirements, Investigator site staff will not be given access to the EDC system until they have been trianed. Automatic validation programs check for data discrepancies in the eCRFs. The EDC system allows modification and/or verification of the entered data by the investigator staff.

The investigator/designee is responsible for assuring that the data (entered into eCRF) is complete, accurate, and that entry and updates are performed in a timely manner. The Investigator must certify that the data entered are complete and accurate. After final database lock, the investigator will receive copies of the participant data for archiving at the investigational site.

All data should be recorded, handled, and stored in a way that allows its accurate reporting, interpretation, and verification.

11.2 Database management and quality control

Novartis personnel will review the data entered by investigational staff for completeness and accuracy. Electronic data queries stating the nature of the problem and requesting clarification will be created for discrepancies and missing values and sent to the investigational site via the EDC system. Designated investigator site staff are required to respond promptly to queries and to make any necessary changes to the data.

Concomitant medications and prior medications entered into the database will be coded using the World Health Organization (WHO) Drug Reference List, which employs the Anatomical Therapeutic Chemical classification system. Medical history/current medical conditions, concomitant and prior procedures/non-drug therapies, and adverse events will be coded using the Medical Dictionary for Regulatory Activities (MedDRA) terminology.

Confidential

Randomization/re-randomization codes and data about all study treatment(s) dispensed to the participant and all dosage changes will be tracked using an IRT. The system will be supplied by a vendor, who will also manage the database. The data will be sent electronically to Novartis at specific timelines.

Each occurrence of a code break via IRT will be reported to the clinical team and monitor. The code break functionality will remain available until study shut down or upon request of Novartis.

Once all the necessary actions have been completed and the database has been declared to be complete and accurate, it will be locked **and the treatment codes will be unblinded** and made available for data analysis. Any changes to the database after that time can only be made after written agreement by Novartis development management.

11.3 Site monitoring

Before study initiation, at a site initiation visit or at an investigator's meeting, a Novartis representative will review the protocol and data capture requirements (i.e., eCRFs) with the investigators and their staff. During the study, Novartis employs several methods of ensuring protocol and GCP compliance and the quality/integrity of the sites' data. The field monitoring will be performed according to relevant sections of the monitoring plan. Monitors will visit the site to check the completeness and appropriate storage of investigator site files, participant records, the accuracy of data capture / data entry, the adherence to the protocol, to the study procedures and to Good Clinical Practice. The monitor is also responsible to report any deviation from the protocol or defined procedures and to follow the progress of enrollment. Monitors are responsible to ensure that study treatment is being stored, dispensed, and accounted for according to specifications. Key study personnel must be available to assist the field monitors during these visits. Continuous remote monitoring of each site's data may be performed by a centralized Novartis/CRA (Clinical Research Associate) organization. Additionally, a central analytics organization may analyze data and identify risks and trends for site operational parameters, and provide reports to Novartis clinical teams to assist with trial oversight.

The investigator must maintain source documents for each participant in the study, consisting of case and visit notes (hospital or clinic medical records) containing demographic and medical information, laboratory data, electrocardiograms, and the results of any other tests or assessments. All information on eCRFs must be traceable to these source documents in the participant's file. The investigator must also keep the original informed consent forms signed by the participant (a signed copy is given to the participant). The investigator must give the monitor access to all relevant source documents in paper or electronic format to confirm their consistency with the data capture and/or data entry. Novartis monitoring standards require full verification for the presence of informed consent, adherence to the inclusion/exclusion criteria, documentation of SAEs, and of data that will be used for all primary variables. Additional checks of the consistency of the source data with the eCRFs are performed according to the study-specific monitoring plan. No information in source documents about the identity of the participants will be disclosed.

12 Data analysis and statistical methods

The primary endpoint analysis will be performed after all participants complete Week 16 as described in Section 12.7 and the final analysis will be conducted on all participant data at the time the study ends. Any data analysis carried out independently by the investigator should be submitted to Novartis before publication or presentation.

Summary statistics for continuous variables will generally include the number of participants (N), minimum, lower quartile, mean, standard deviation (SD), median, upper quartile, and maximum. For binary or discrete variables the absolute number of participants in each category and relative frequencies will be provided.

In case of a global health disruptive event, such as pandemic/epidemic (e.g., COVID-19), affecting the ability of the patient or the site to adhere to protocol requirements and assessments and therefore leading to a potential increase in the number of missing measurements, additional anyalysis populations may be defined as per the instructions and procedures outlined in Section 16.9.

The efficacy evaluation of secukinumab relative to placebo will generally focus on the first 16 weeks of treatment unless otherwise specified.

Data analyses will be presented by treatment group. Efficacy and safety data for the 16-week placebo-controlled period and the entire treatment period as appropriate will be presented by the following two treatment groups. participants may be included in more than one treatment group for some analyses (e.g., exposure adjusted adverse events over the entire treatment period).

These treatment groups represent the regimens to which participants will be eligible to be randomized:

- Secukinumab 150 mg regimen
- Placebo regimen

Note that the treatment groups above for a participant may differ depending on the time period of the analysis and whether one assesses the participant for efficacy or safety (see Section 12.1 for details).

Data may also be presented by a combination of the 'original' and 'switch' treatment groups. These treatment groups represent the treatment combinations the participants experience over the course of the entire trial.

[figure not shown]
12.1 Analysis sets

The following analysis sets will be used in this study:

Randomized set: The randomized set will be defined as all participants who were randomized. Unless otherwise specified, mis-randomized participants (mis-randomized in IRT) will be excluded from the randomized set.

Mis-randomized participants are defined as those participants who were mistakenly randomized into the IRT prior to the site confirming all eligibility criteria had been met and to whom no study medication was given. Mis-randomized participants are treated as screen failures.

Full analysis set (FAS): The FAS will be comprised of all participants from the randomized set to whom study treatment has been assigned. Following the intent-to-treat principle, participants will be evaluated according to the treatment assigned to at randomization. Three subsets of FAS are defined as follows:

Safety set: The safety set includes all participants who took at least one dose of study treatment during the treatment period. participants will be evaluated according to treatment received.

12.2 Participant demographics and other baseline characteristics

Demographics and BSL characteristics

Summary statistics will be presented for continuous demographic and BSL characteristic variables for each treatment group and for all participants in the randomized set. The number and percentage of participants in each category will be presented for categorical variables for each treatment group and all participants.

The following demographic variables and BSL disease characteristics will be summarized by treatment groups:

- Gender, age, race, ethnicity, weight, height, and Body Mass Index (BMI)
- Anti-TNF treatment history (naïve or inadequate responder), ACR components and other disease-related measures (e.g., DAS28, presense of dactylitis, presense of enthesitis, time since first diagnosis of PsA, participant with psoriasis ≥ 3%), etc., number of prior biologic PsA therapies, dose of MTX or other DMARD at randomization.

Medical history

A history of PsA with focus on previous extra-articular involvement and past therapies for PsA will be obtained and summarized by treatment group. Any other significant prior or active medical condition at the time of signing informed consent will be recorded and coded using the MedDRA dictionary. These medical conditions will be summarized by primary system organ class and preferred term.

To establish a BSL level of cardiovascular risk, the number and percentage of participants with pre-solicited cardiovascular risk factors will be summarized by treatment group. The number of cardiovascular risk factors that each participant has will also be summarized by treatment group. If it is unknown whether or not a participant currently or previously experienced a specific cardiovascular risk factor, it will be assumed that cardiovascular risk factor did not occur for that participant.

12.3 Treatments

Study treatment

The analysis of study treatment data will be based on the safety set. The number of visits with active and placebo injections received will be presented by treatment group.

The duration of exposure to study treatment will also be summarized by treatment group. In addition, the number and percentage of participants with cumulative exposure levels (e.g., any exposure, ≥ 1 weeks, ≥ 2 weeks, ≥ 3 weeks, ≥ 4 weeks, ≥ 8 weeks, etc.) will be presented.

Prior and concomitant medication

Prior and concomitant medications will be summarized in separate tables by treatment group.

Prior medications are defined as treatments taken and stopped prior to first dose of study treatment. Any medication given at least once between the day of first dose of randomized study treatment and the date of the last study visit will be a concomitant medication, including those which were started pre-BSL and continued into the period where study treatment is administered.

Medications will be presented in alphabetical order, by Anatomical Therapeutic Classification (ATC) codes and grouped by anatomical main group. Tables will show the overall number and percentage of participants receiving at least one treatment of a particular ATC code and at least one treatment in a particular anatomical main group.

Significant prior and concomitant non-drug therapies and procedures will be summarized by primary system organ class and MedDRA preferred term.

Prior surgeries and procedures are defined as surgeries and procedures done prior to first dose of study treatment. Any surgeries and procedures done between the day of first dose of study treatment and within the date of the last study visit will be a concomitant surgeries and procedures, including those which were started pre-BSL and continued into the period where study treatment is administered.

The number and percentage of participants receiving prior and concomitant PsA therapy will be presented by randomized treatment group as well as the reasons for stopping their therapies (primary lack of efficacy, secondary lack of efficacy, lack of tolerability, other) and the total duration of exposure to PsA therapies previously. NSAID, glucocorticoid and DMARD (MTX, Leflunomide, Sulfasalazine) use will be summarized.

12.4 Analysis of the primary endpoint(s)/estimand(s)

The primary objective of this study is to assess the efficacy of secukinumab relative to placebo at week 16 based on the proportion of participants achieving an ACR20 response. The consistency of the treatment difference between this bridging study and the global study will be evaluated.

12.4.1 Definition of primary endpoint(s)/estimand(s)

The primary efficacy variable will be ACR20 response at Week 16. The analysis of the primary efficacy variable will be based on the FAS . Primarily, CRP will be used instead of ESR to calculate ACR response; ESR will only be used in the event CRP is missing.

12.4.2 Statistical model, hypothesis, and method of analysis

The primary analysis of ACR20 at Week 16 in the FAS will be evaluated using a logistic regression with treatment as a factor and weight as a covariate. Difference in response proportions between secukinumab regimen and placebo regimen and the corresponding 95% confidence interval (CI) will be computed utilizing the logistic regression model fitted.

12.4.3 Handling of missing values/censoring/discontinuations

Missing data for ACR20 response and other binary efficacy variables (e.g., ACR50, etc.) for data up to Week 16 will be handled as follows:

- 1. participants who discontinue from treatment or study for any reason will be considered as non-responders from the time of discontinuation through Week 16
- 2. participants who do not have the required data to compute ACR responses (i.e., tender and swollen joint counts and at least three of the five ACR core set variables) at BSL and at the specific timepoint will be classified as non-responders at the specific timepoint.

participants who are unblinded prior to the scheduled time point will be considered nonresponders from the time of unblinding up to Week 16. The primary analysis will use the nonresponder imputation.

Continuous variables (e.g., ACR components, etc.) will be analyzed using a mixed-effects model repeated measures (MMRM) which is valid under the missing at random (MAR) assumption. As such, single-point imputation of missing data will not be performed (e.g., LOCF). For analyses of these parameters, if all post-BSL values are missing then these missing values will not be imputed and this participant will be removed from the analysis of the corresponding variable, i.e., it might be that the number of participants providing data to an analysis is smaller than the number of participants in the FAS.

12.4.4 Sensitivity analyses for primary endpoint/estimand

Sensitivity analysis will be conducted in order to provide evidence that the results seen from the primary analysis are robust. These analyses will center on the deviations in model assumptions and the handlingof missing data.

In order to determine the robustness of the logistic regression model used for the primary analysis, ACR20 response in active PsA participants at Week 16 will also be evaluated using a non-parametric regression (Koch et al (1998) model with the same independent variables as the logistic regression model.

The impact of missing data on the analysis results of ACR20 in active PsA participants will be assessed as well by repeating the logistic regression model using different ways to handle missing data. This may include, but are not limited to:

- Multiple imputation
- Observed data analysis

12.4.5 Supplementary analysis

Supplementary analysis will be conducted in order to fully investigate and understand the treatment effects as well as demonstrate the consistency between the bridging study and the global study.

The analyses may include, but are not limited to:

- Meta-analysis: it combines the estimates of the treatment effect from the historical studies and delivers an overall treatment effect as well as the corresponding confidence interval. The consistency can be claimed if the treatment effect estimated from the bridging study is located within the confidence interval.
- Bayesian Meta-Analytic-Predictive (MAP) approach: it is similar as the meta-analysis, but priors should be specified carefully.
- Logistic regression: same logistic regression model will be used as the primary analysis. The odds ratio bewteen the secukinumab regime and the placebo regimen and the corresponding 95% confidence interval will be presented.

Subgroup analysis of the primary endpoint will be conducted by selected subgroup groups. The subgroups to be considered will be defined in the SAP.

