1.2 Purpose

The purpose of this bridging study is to assess the efficacy and safety of secukinumab 150 mg s.c. in Chinese participants with active PsA compared to placebo to support registration in China. The clinical data in this study will be used for the extrapolation between Chinese population and global population by demonstrating that the treatment difference in ACR20 response rates between Secukinumab 150mg s.c. and placebo in Chinese participants at Week 16 is consistent with that observed in global studies.

2 Objectives and endpoints

Table 2-1Objectives and related endpoints

| Objective(s) | Endpoint(s) |
|--|--|
| Primary objective(s) | Endpoint(s) for primary objective(s) |
| • To demonstrate the treatment effect of secukinumab 150 mg s.c. (q1w×4, followed by dosing q4w) in Chinese subjects with active PsA is consistent with global population by assessing American College of Rheumatology 20 (ACR20) response rates in participants treated with secukinumab 150 mg s.c. compared to placebo s.c. at Week 16. | ACR20 response at Week 16. A patient will be considered as improved according to the ACR20 criteria if he/she has at least 20% improvement in the three following measures: Tender joint count; Swollen joint count; and at least 3 of the following 5 domains: a. Patient's assessment of PsA pain b. Patient's global assessment of disease activity c. Physician's global assessment of disease activity d. Health Assessment Questionnaire – Disability Index (HAQ-DI[®]) score Acute phase reactant (hsCRP or ESR) |
| Secondary objective(s) | Endpoint(s) for secondary objective(s) |
| • To evaluate the efficacy of secukinumab 150 mg s.c. (q1w×4, followed by dosing q4w) at Week 16 compared with placebo by assessing the proportion of subjects achieving an ACR50 response. | • ACR50 response rate at Week 16. |
| • To evaluate the efficacy of secukinumab 150 mg s.c. (q1w×4, followed by dosing q4w) at Week 16 compared with placebo by assessing the changes from BSL in Disease Activity Score for 28 joints - C reactive protein (DAS28-CRP). | • Change from BSL in DAS28-CRP at Week 16. |
| • To evaluate the efficacy of secukinumab 150 mg s.c. (q1w×4, followed by dosing q4w) at Week 16 compared with placebo by assessing change from BSL in PASDAS | Change from BSL in PASDAS at Week 16. |

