12.8 Sample size calculation

12.8.1 **Primary endpoint(s)**

As it is a bridging study for China registration, this study will pursue an estimation strategy rather than formal hypothesis testing of treatment difference.

Analysis of the pooled data of global pivotal studies (CAIN457F2312, CAIN457F2318, CAIN457F2336 and CAIN457F2342) showed an active drug response rate of about 51.4% and a placebo response rate of 23.1% after 16 weeks for ACR20. With 40 participants (1:1 ratio to two arms), there are approximately 86.0% probability to show at least 50% global treatment difference (14.15%) and approximately 96.0% probability to show positive treatment difference.

Table 12-1 shows the probability of success with different observed response rates.

| | | | | | | - | | |
|------------|-----------------------------------|------------------|------------------------|----------------------|----------------------------------|-------|----------------------------------|-------|
| | Observed Res | ponse Rat | е | | Criterion 1 | | Criterion 2 | |
| | Secukinuma b (p ₁) | Placeb o (p₂) | p 1 -p 2 | 95% CI of (p1-p2) | Aimed Treatment Difference | PoS | Aimed Treatment Difference | PoS |
| Scenario 1 | 0.464 | 0.231 | 0.233 | (-0.053, 0.519) | > 0.1415 | 0.772 | > 0 | 0.922 |
| Scenario 2 | 0.514 | 0.231 | 0.283 | (-0.003, 0.569) | > 0.1415 | 0.860 | > 0 | 0.960 |
| Scenario 3 | 0.564 | 0.231 | 0.333 | (0.048, 0.618) | > 0.1415 | 0.922 | > 0 | 0.981 |
| Scenario 4 | 0.614 | 0.231 | 0.383 | (0.101, 0.665) | > 0.1415 | 0.961 | > 0 | 0.992 |

 Table 12-1
 Probability of Success with Different Observed Response Rates

13 Ethical considerations and administrative procedures

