2.5 Analysis of the primary objective

The primary objective of this study is to assess the efficacy of secukinumab relative to placebo at week 16 based on the proportion of participants achieving an ACR20 response. The consistency of the treatment difference between this bridging study and the pooled efficacy data of global pivotal studies (CAIN457F2312, CAIN457F2318, CAIN457F2336 and CAIN457F2342) were evaluated at the Primary endpoint analysis and will not be repeated at the Final Analysis.

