2.5.4 Supportive analyses

The supportive analyses have been presented in the SAP for Primary endpoint analysis and will not be repeated in this document.

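### The supplementary consistency condition in Protocol 12.4.5 ignores the bridging study's own sampling error, so it is often missed even when the Chinese and global effects are identical

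*Protocol*

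**What the plan says.** Protocol 1.2 makes agreement with the global programme the purpose of the study: to show that the ACR20 treatment difference "in Chinese participants at Week 16 is consistent with that observed in global studies". Protocol 12.4.5 gives supplementary analysis two tasks, to understand the treatment effect "as well as demonstrate the consistency between the bridging study and the global study". Its list of methods is open: "The analyses may include, but are not limited to". The first item is a meta-analysis that combines the historical studies into an overall effect with a confidence interval, followed by the condition: "The consistency can be claimed if the treatment effect estimated from the bridging study is located within the confidence interval". The next item is a Bayesian meta-analytic-predictive (MAP) approach, with no rule of its own.

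The primary analysis (Protocol 12.4.2) is separate: a logistic-regression difference in proportions with a 95% CI. On inference, Protocol 12.8.1 says "this study will pursue an estimation strategy rather than formal hypothesis testing of treatment difference". It gives probabilities for two other targets, an observed difference above 14.15 percentage points (half the global difference) and one above zero. It gives none for the interval condition.

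SAP 2.5 says that consistency with the pooled data of four global studies has been assessed: the evaluations "were evaluated at the Primary endpoint analysis and will not be repeated at the Final Analysis". On supportive methods, SAP 2.5.4 says: "The supportive analyses have been presented in the SAP for Primary endpoint analysis and will not be repeated in this document". That other SAP is not among the documents.

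**The concern.** The condition compares a point estimate from 40 patients with an interval built only from the historical studies. The bridging study's error is the larger of the two and appears nowhere in the comparison. Three consequences follow:

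- A Chinese effect exactly equal to the global one will often fall outside by chance.
- The condition can be missed because the Chinese estimate is higher than the global one.
- Under a common-effect model, adding global data narrows the target and makes the condition harder to meet.

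This is the only sentence in the supplied documents that says when consistency can be claimed, and consistency is what the study is for. If the condition is applied, a miss mostly reflects the size of the bridging study.

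**Working it through.** **Inputs.** Response rates 51.4% and 23.1%, difference 0.283 (Protocol 12.8.1); 20 per arm (Protocol 6.1.3); 95% level (SAP 2.1 default, since 12.4.5 gives none). Not in the documents, so assumed: historical patients per arm, meta-analysis model and between-study SD (tau). Calculations use unadjusted proportions and ignore the weight covariate.

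Historical size is taken as 100 to 800 per arm. The value 348 is (397 + 996)/4, from the two pooled studies whose totals appear in Protocol 1.1, with four equal arms assumed.

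**1. The plan's own figures.** Variance term: 0.514×0.486 + 0.231×0.769 = 0.2498 + 0.1776 = 0.4274. Bridging SE = √(0.4274/20) = 0.1462. The interval 0.283 ± 1.96×0.1462 is about (-0.004, 0.570), against (-0.003, 0.569) in Table 12-1, a rounding difference. Exact enumeration of two Binomial(20) arms gives 0.860 for a difference above 0.1415 and 0.960 for one above zero. Both match Table 12-1.

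**2. Common-effect interval, identical effects.** SE_h = √(0.4274/n); half-width h = 1.96×SE_h. The normal approximation is

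P(miss) = 2×[1 − Φ(1.96×SE_h / √(SE_h² + 0.1462²))].

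At n = 348: SE_h = 0.0350 and √(0.0350² + 0.1462²) = 0.1503. The ratio is 1.96×0.0350/0.1503 = 0.457, so P(miss) = 0.648. Exact enumeration of the bridging arms, with a normal historical estimate, gives:

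| Historical n per arm | h | Missed | Estimate above interval |
|---|---|---|---|
| 100 | 0.128 | 42.5% | 21.4% |
| 200 | 0.091 | 55.6% | 28.1% |
| 348 | 0.069 | 64.9% | 32.8% |
| 800 | 0.045 | 76.0% | 38.5% |

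About half of the misses lie above the interval.

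**3. Random-effects interval, identical effects.** Simulation: four equal studies, binomial data, Chinese effect held at the global mean. Percent missed, DerSimonian-Laird / Hartung-Knapp, good to about one point:

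| Total per arm | tau 0 | tau 0.10 | tau 0.20 |
|---|---|---|---|
| 100 | 38 / 29 | 35 / 22 | 28 / 14 |
| 200 | 51 / 41 | 44 / 27 | 31 / 15 |
| 800 | 73 / 65 | 53 / 34 | 33 / 17 |

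**4. Against the 14.15-point criterion** (common effect; n = 100 / 200 / 348 / 800):

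- Identical effects: that criterion met but the interval condition missed, 30 / 42 / 51 / 62%; the reverse, 1.5 / 0.1 / 0.0 / 0.0%.
- Half the effect (0.3725 vs 0.231): interval condition met 42 / 31 / 24 / 16%; 14.15-point criterion 55%.
- No effect: interval condition met 14.6 / 8.2 / 5.5 / 3.2%; 14.15-point criterion 17%.

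The interval condition is almost nested inside the other. They are a strict and a loose benchmark, not contradictory ones.

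**5. An interval carrying both errors.** Bridging minus global, half-width 1.96×√(0.4274/20 + 0.4274/n) = 0.314 / 0.301 / 0.295 / 0.290. Using the observed bridging variance, it includes zero in 93% to 94% of trials with identical effects, but also in 43% to 50% with no Chinese effect. The matching predictive interval for a 20/20 study at n = 348 is 0.283 ± 0.295, or -0.012 to 0.578.

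**The case against.** The strongest reply is that a miss has no stated consequence. The sentence is a sufficient condition in a list of methods that may or may not be used, under an estimation strategy. A reader might infer that a miss blocks a consistency claim or shows inconsistency; no passage says either. That stands, and it limits the point to withheld claims and misses that carry little information.

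Nor is the condition weak support when it is met. At 348 per arm it is met in 35.1% of trials with identical effects and 5.5% with none, a ratio of about 6.4; the 14.15-point criterion gives 86.0% and 17.3%, about 5.0. So the inference that the condition invites false claims is not supported either.

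A reader might also infer that this rule decided the Week 16 evaluation. The documents do not show it. SAP 2.5 speaks of pooled global data, which fits the half-of-global benchmark in 12.8.1 at least as well as a meta-analysis interval, and it names no rule. The Week 16 SAP may have changed or dropped the item.

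Finally, the bridging error is visible elsewhere, in the primary 95% CI, and a predictive method is already listed. Both are true, but neither puts that error into the sentence that says when consistency can be claimed.

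**Conclusion.** The point holds in limited form and should be fixed. As written, the condition omits the dominant source of error and is missed far more often than 5% of the time when effects are identical, in every scenario tried: 42% to 76% under a common effect, about 28% to 73% with DerSimonian-Laird and 14% to 65% with Hartung-Knapp. The ends of these ranges depend on assumed historical size, model and tau; the 14% is the low end of the scenarios run, not a floor. Confidence in the mechanism is high. Confidence in the practical effect is medium, because the Week 16 SAP is not available. The primary analysis and the 12.8.1 probabilities are untouched.

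**What to change.** Delete the condition sentence in Protocol 12.4.5. In its place report, as descriptive support only, either the bridging-minus-global difference with a 95% interval carrying both errors, or a predictive interval for a 20/20 study from the MAP item already listed. Make neither a pass/fail rule: the first often includes zero even with no Chinese effect, and the second contains a zero treatment difference.

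Because the Week 16 evaluation is done, label any added interval post hoc, state which rule supported any consistency statement, and do not read a miss of the interval condition as evidence of inconsistency. Do not adopt the 14.15-point criterion retrospectively. If it was the rule used, print its claim rates beside it: 86% with identical effects, 55% with half the effect and 17% with none.

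The cost is wording and one interval from existing output, with no new data. The drawback is that the interval is wide and shows how little 40 patients can discriminate.
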